**Table 4: Safety/Tolerability Assessment Timeline** 

Safety/Tolerability Evaluation #	Day 1	Day 8	Day 15	Day 22	Day 29	Day 64	Day 195	Day 380
SAEs								
Solicited AEs*								
Clinical Safety Lab AEs								
Unsolicited non-serious AEs								
AESIs (PIMMCs)								
MAAEs								

#Note that all visits after Visit 3 are based on the day that Visit 3 occurs. If it occurs on Day 15, all subsequent visits and windows are as written in the Table. If it occurs after Day 15, subsequent visit days will be adjusted to maintain the intervals. For example, if Visit 3 occurs on Day 16, then the remaining target Days are 23, 30, 65, 196, and 381. The dates as written in the Table reflect the schedule assuming that Visit 3 occurs on Day 15.

\*Solicited AEs may require recording beyond Days 8 and 22, if they persist.

## 9.2 Methods and Timing for Assessing, Recording, and Analyzing Safety Parameters

#### 9.2.1 Adverse Events

**Adverse Event (AE):** ICH E6 (R2) GCP defines an AE as any untoward medical occurrence in a patient or clinical investigation participant administered a pharmaceutical product and which does not necessarily have a causal relationship with this treatment. The FDA defines an AE as any untoward medical occurrence associated with the use of a drug in humans, whether or not considered drug related.

An AE can therefore be any unfavorable and unintended sign (including an abnormal laboratory finding), symptom, or disease temporally associated with the use of a medicinal (investigational) product. The occurrence of an AE may come to the attention of study personnel during study visits and interviews of a study recipient presenting for medical care, or upon review by a study monitor.

AEs, including solicited injection site and systemic (subjective and quantitative) reactions, not meeting the protocol-defined criteria for SAEs, will be recorded on the appropriate eCRF. Information to be collected for unsolicited non-serious AEs includes event description, date of onset, licensed study physician's assessment of severity and relationship to study product or alternate etiology (if not related to study product) (assessed only by those with the training and authority to make a diagnosis and listed on the Form FDA 1572 as the site PI or sub-investigator), date of resolution, seriousness, and outcome. AEs occurring during the trial-collection and reporting period will be documented appropriately regardless of relationship to study product. AEs will be followed through resolution.

Any medical condition that is present at the time that the participant is screened will be considered as baseline and not reported as an AE. However, if the severity of any pre-existing medical condition increases, it will be recorded as an AE.

AEs must be assessed for severity and relationship to study product (see definitions below). AEs characterized as intermittent require documentation of onset and duration of each episode. The start and stop date of each reported AE will be recorded on the appropriate eCRF.

Medically-Attended Adverse Events (MAAEs): For each unsolicited AE experienced, the participant will be asked if he/she had received medical attention, defined as hospitalization, an emergency room visit, or an otherwise unscheduled visit to or from medical personnel for any reason. AEs characterized by such unscheduled medical care will be designated as MAAEs.

Adverse Events of Special Interest (AESI): An adverse event of special interest (serious or nonserious) is one of scientific and medical concern specific to the sponsor's product or program, for which ongoing monitoring and rapid communication by the investigator to the sponsor can be appropriate. Such an event might warrant further investigation in order to characterize and understand it. Depending on the nature of the event, rapid communication by the trial sponsor to other parties (e.g., regulators) might also be warranted.

**Potentially Immune-Mediated Medical Conditions (PIMMCs):** PIMMCs constitute a group of AEs that includes diseases which are clearly autoimmune in etiology and other inflammatory and/or neurologic disorders which may or may not have autoimmune etiologies. PIMMCs are presented in Appendix B: Adverse Events of Special Interest. This is the only category of AESIs that will be collected for this trial.

**Protocol Specified AESIs:** The only protocol-specific AESIs are those PIMMCs listed in Appendix B.

**Severity of Event:** AEs will be assessed by a licensed study physician listed on the Form FDA 1572 as the site PI or sub-investigator using a protocol-defined grading system (see Sections 9.2.2 and 9.2.3). For events not included in the protocol-defined grading system, the following guidelines will be used to quantify severity:

- Mild (Grade 1): Events require minimal or no treatment and do not interfere with the participant's daily activities.
- Moderate (Grade 2): Events result in a low level of inconvenience or concern with therapeutic measures. Moderate events may cause some interference with functioning and daily activities.

• Severe (Grade 3): Events interrupt the participant's daily activities and may require systemic drug therapy or other treatment. Severe events are usually incapacitating.

**Relationship to Study Product:** The licensed study physician's assessment of an AE's relationship to study product is part of the documentation process, but it is not a factor in determining what is or is not reported in this trial. If there is any doubt as to whether a clinical observation is an AE, the event should be reported. The relationship to study product must be assessed for AEs using the terms: related or not related. In a clinical trial, the study product must always be suspect. To help assess, the following guidelines are used:

- Related There is a reasonable possibility that the study product caused the AE. Reasonable possibility means that there is evidence to suggest a causal relationship between the study product and the AE.
- Not Related There is not a reasonable possibility that the administration of the study product caused the event.

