**Table 1: Study Objectives and Outcome Measures** 

Primary Objective: Safety	Primary Safety Outcome Measures

 
To assess the safety of lyophilized and liquid formulations of AV7909.
 
	Occurrence of all SAEs through approximately 12 months following receipt of the second study vaccination (approximately Day 380).
	
 
Occurrence of abnormal clinical safety laboratory AEs at approximately Day 29.
 

	Occurrence of all protocol specified AESIs (i.e., PIMMCs) and MAAEs, from the time of the first study vaccination through approximately 12 months following the second vaccination (approximately Day 380).
	Occurrence of unsolicited non-serious adverse events from the time of the first study vaccination through approximately Day 64.
Primary Objective: Tolerability	Primary Tolerability Outcome Measures
To assess the tolerability of lyophilized and liquid formulations of AV7909.	Occurrence of solicited injection site and systemic reactogenicity events in the week after each study vaccination (Days 1 through 8 and Days 15 through 22, inclusive).
Secondary Objective: Immunogenicity	Secondary Immunogenicity Outcome Measures
To obtain initial estimate of comparative immunogenicity of liquid and lyophilized formulations of AV7909.	• Geometric mean titer and 95% confidence intervals of antibodies assayed by toxin neutralization assay (ED 50 and NF 50 ) and anti-PA IgG by ELISA in each study group before vaccination and on approximately Days 8, 15, 22, 29, 64, 195, and 380.
	• Proportion and 95% confidence intervals of participants in each study group with seroconversion for antibodies detected by TNA and ELISA (defined as a ≥4-fold increase over baseline levels, or a ≥4-fold increase over the lower limit of quantification [LLOQ] if the baseline value is < LLOQ) on approximately Days 8, 15, 22, 29, 64, 195, and 380.
	• Proportion and 95% confidence intervals of participants in each study group with putative seroprotection (defined as NF 50 ≥ 0.56) before vaccination and on approximately Days 8, 15, 22, 29, 64, 195, and 380.
Exploratory Immunogenicity Objectives	Exploratory Immunogenicity Study Outcomes
Exploratory Immunogenicity Objectives	

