## 7 STUDY PROCEDURES/EVALUATIONS

#### 7.1 Clinical Evaluations

A complete medical history will be obtained by interview of participants at the screening visit. Participants will be queried regarding a history of significant medical disorders of the head, eyes, ears, nose, throat, cardiovascular system, lungs, gastrointestinal tract, liver, pancreas, kidney, urologic system, nervous system, blood, lymph nodes, endocrine system, musculoskeletal system, skin, and genital/reproductive tract. A history of any allergies, cancer, immune deficiency, psychiatric illness, substance abuse, autoimmune disease, and any other significant medical history will be solicited. At all subsequent visits, an interim medical history will be obtained by interview of participants and any changes since the previous clinic visit or phone call will be noted, when within the respective reporting period. The interim medical history will include an assessment for new medical conditions, MAAEs, and symptoms suggestive of AESIs (PIMMCs).

Concomitant medications will be collected as described in Section 6.5.

At the screening visit, a physical examination will be performed on all participants, by a study clinician licensed to make medical diagnoses and listed on the Form FDA 1572 as the site PI or sub-investigator, to include the following organs and organ systems: abdomen, cardiovascular/heart, extremities, general appearance, HEENT, hepatobiliary/spleen, lymph nodes, musculoskeletal, neck, neurological, pulmonary/chest, and skin. Specific attention will be placed in assessing for physical signs of PIMMCs. At the vaccination visit and at follow-up visits after each study vaccination, a targeted physical examination may be performed by a study clinician licensed to make medical diagnoses and listed on the Form FDA 1572 as the site PI or sub-investigator, if indicated, based on the participant's interim medical history. Targeted physical examinations should also include an assessment for signs suggestive of PIMMCs.

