## 9.2.2 Reactogenicity

Reactogenicity events are solicited AEs that are common and known to occur following administration of this type of study vaccine. The following Toxicity Grading Scales will be used to grade solicited injection site and systemic (subjective and quantitative) reactions:

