**Table 7: Subjective Systemic Reactogenicity Grading** 

Systemic (Subjective)	Mild (Grade 1)	Moderate (Grade 2)	Severe (Grade 3)
Feverishness	No interference with daily activity	Some interference with daily activity	Significant interference, prevents daily activity
Fatigue	No interference with daily activity	Some interference with daily activity	Significant interference, prevents daily activity
Malaise	No interference with daily activity	Some interference with daily activity	Significant interference, prevents daily activity

Systemic (Subjective)	Mild (Grade 1)	Moderate (Grade 2)	Severe (Grade 3)
Myalgia*	No interference with daily activity	Some interference with daily activity	Significant interference, prevents daily activity
Arthralgia*	No interference with daily activity	Some interference with daily activity	Significant interference, prevents daily activity
Headache	No interference with daily activity	Some interference with daily activity	Significant interference, prevents daily activity or headache requires prescription medication
Nausea	No interference with daily activity	Some interference with daily activity	Significant interference, prevents daily activity or nausea requires prescription medication

\* Not at injection site.

Oral temperature# will be graded as follows:

Table 8: Quantitative Systemic (Oral Temperature) Reactogenicity Grading

Systemic (Quantitative)	Mild (Grade 1)	Moderate (Grade 2)	Severe (Grade 3)
Fever* – oral†	38.0°C – 38.4°C	38.5°C – 38.9°C	>38.9°C
rever - oran	100.4°F – 101.1°F	101.2°F – 102.0°F	>102.0°F

<sup># Oral temperature assessed on Day 1 prior to the first study vaccination will be considered as baseline.

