# 9.4. Deaths, Serious Adverse Events, and other Significant Adverse Events

The following listings will be presented including Subject ID, Age (years) AE Description, AE Onset Date/End Date, Last Vaccination Received/Days Post Vaccination, Reason Reported as an SAE, Relationship to Treatment, Alternate Etiology if not Related, Outcome, and Duration of Event (days):

- Deaths and serious adverse events (Table 51).
- Other significant adverse events, including AESIs/PIMMCs and MAAEs (Table 53).

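### The medical-attention question is set only for unsolicited AEs, although the MAAE designation and the primary MAAE outcome are not so limited, so a briefly attended solicited reaction may be missed or captured inconsistently

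*Protocol*

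**What the plan says.** Protocol Section 9.2.1 sets the question: "For each unsolicited AE experienced, the participant will be asked if he/she had received medical attention". Medical attention there means hospitalisation, an emergency room visit or any other unscheduled contact with medical personnel. The designation follows at once: "AEs characterized by such unscheduled medical care will be designated as MAAEs".

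The same section brings solicited reactions within the AE concept ("AEs, including solicited injection site and systemic (subjective and quantitative) reactions, not meeting the protocol-defined criteria for SAEs"), and Section 9.2.2 repeats this: "Reactogenicity events are solicited AEs that are common and known to occur following administration of this type of study vaccine".

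The primary safety outcomes in Protocol Table 1 include "Occurrence of all protocol specified AESIs (i.e., PIMMCs) and MAAEs, from the time of the first study vaccination", running to about Day 380. SAP Section 3.2.1 carries the same outcome. Neither place makes an exception for solicited reactions.

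In the SAP, MAAEs appear as one row of Table 33, which does not say whether solicited events count, and in the Table 53 listing, which has MedDRA system organ class and preferred term columns. Protocol Section 11.6.2 describes MedDRA coding for unsolicited AEs.

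**The concern.** The question covers a narrower set of events than the designation. Whether a solicited reaction that took someone to an emergency room is an MAAE depends on which of two adjacent sentences the site follows, and only the narrower one tells staff to ask.

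The protocol foresees that solicited reactions may need care. Grade 3 headache, for example, is "Significant interference, prevents daily activity or headache requires prescription medication", and grade 3 pain, tenderness, pruritus and nausea can likewise be met by a need for prescription medication.

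Attended reactions in the week after a dose are among the MAAEs most plausibly caused by vaccination, and comparing the two formulations is a stated aim of the design. The site asks the same question in both arms and assessors are blinded, so the gap is not itself biased towards one product. If one formulation were more reactogenic, however, under-capture would fall mainly on that arm and shrink the difference in MAAEs.

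**Working it through.** This is mainly a comparison of texts. The documents state no MAAE rate, so there is no plan figure for this point to reproduce.

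**Step 1: scope of each statement.**
- Question (Protocol 9.2.1): unsolicited AEs.
- Designation (Protocol 9.2.1, next sentence): AEs.
- Solicited reactions are AEs (Protocol 9.2.1 and 9.2.2): 6 injection-site plus 8 systemic items, 14 in all.
- Primary outcome (Protocol Table 1; SAP 3.2.1): MAAEs, without limitation.

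**Step 2: follow one case.** Take a severe headache on Day 2, an emergency visit without admission, and resolution by Day 5.
- The 9.2.1 question does not apply, because headache in that window is solicited.
- The rule that ongoing reactions become AEs (Protocol 8.2.1 and 8.2.3) does not apply, because the reaction has resolved. Section 2.3.1 says earlier local reactions often resolved within 48 hours, so resolution before the visit would not be unusual.
- The SAE route (Protocol 9.2.4) would not ordinarily apply without admission, unless the event is judged an important medical event.
- The interim history assesses MAAEs (7.1), and all MAAEs are to be recorded at the Day 8, 15 and 22 visits (8.2.1 to 8.2.3). Both rely on the 9.2.1 definition.
- New medication should prompt an MAAE evaluation (6.5), but only if a medication was taken and reported.
- A potential grade 3 diary entry triggers an alert and attempted site follow-up (Protocol Section 12), but no medical-attention item is specified for that contact.

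The case may be caught, but no step sets the medical-attention question for it.

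**Step 3: scale.** Inputs are n = 20 per arm and 40 in total (Protocol 11.4.3). The exact 95% interval for x of n has lower limit Beta(0.025; x, n−x+1) and upper limit Beta(0.975; x+1, n−x). As a check on the method, 10/20 gives 27.2 to 72.8% and 20/40 gives 33.8 to 66.2%, which match Protocol Table 12 (27-73 and 34-66).

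The number of attended but unrecorded participants is an assumption, shown for 0, 1 and 2:
- One arm: 0/20 = 0% (0 to 16.8); 1/20 = 5.0% (0.1 to 24.9); 2/20 = 10.0% (1.2 to 31.7).
- Both arms: 0/40 = 0% (0 to 8.8); 1/40 = 2.5% (0.1 to 13.2); 2/40 = 5.0% (0.6 to 16.9).

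Each missed participant thus moves an arm's proportion by 1/20 = 5 points and the pooled proportion by 1/40 = 2.5 points.

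**The case against.** A reader might infer that attended solicited reactions are excluded from the MAAE outcome, or that the plan cannot see medical care in the two solicited weeks. The documents do not support either reading. No section states an exclusion, the designation sentence is not confined to unsolicited AEs, and the routes in step 2 each give the site a chance to learn of the visit. Participants are also told to notify the study center of severe reactions (Protocol 8.1.2 and 8.2.2). That part of the objection stands.

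It is also tempting to cite SAP Listings 10 and 11, which have no medical-attention column for solicited events, as evidence of exclusion. They are not: Listing 12, for unsolicited AEs, has no such column either, although the question is explicitly asked for those events. The eCRF itself is not among the documents.

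The harm is also bounded. Solicited reactions are a primary tolerability outcome in their own right and are tabulated by maximum severity (SAP Tables 40 to 42). A reaction that needed prescription medication is already grade 3 for the five symptoms noted above. Grade 3 solicited events feed the halting rules, and admissions are SAEs. Finally, any count of missed events would rest on assumed rates of grade 3 reactions and of care-seeking, and zero is possible.

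What the objection does not remove is the mismatch in 9.2.1. The safeguards are general prompts, and none sets the medical-attention question for a solicited reaction. Two staff members could follow the text faithfully and record the same event differently.

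**Conclusion.** The point holds as an inconsistency of definition and data capture. Followed as written, Section 9.2.1 can undercount one component of a primary safety outcome, namely solicited reactions that were medically attended, did not lead to admission and resolved before the Day 8 or Day 22 visit. Such events may be missed or captured unevenly; the documents do not establish that they are excluded.

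The size is unknown because no rate is given. The 5-point shift assumes exactly one such participant in an arm of 20, with no other MAAE recorded for that person. Protocol 11.6.2 expects few MAAEs, so one omission would be visible in that row, but solicited severity and SAE reporting are unaffected. Alpha, power and sample size do not change. This is a cheap improvement rather than a defect that undermines the trial.

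**What to change.** - In Protocol 9.2.1, put the question *for each AE experienced, solicited or unsolicited*.
- Add one yes/no medical-attention item to the eMemory Aid reviews already held at Day 8 and Day 22 (or the shifted day after a later second dose).
- MedDRA-code the solicited events flagged in this way, so that they can enter Table 53.
- State in the SAP that the MAAE row of Table 33 and the Table 53 listing include them, and show the unsolicited-only count alongside.

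If the intention is instead to leave solicited reactions out of MAAEs, Protocol Table 1, SAP Section 3.2.1 and the two SAP tables should say so.

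The cost is one wording change, one field at existing visits and a little coding, with a slightly higher MAAE count. SAP 9.3.1 describes solicited collection in the past tense, so collection may already have begun. In that case a late field could give uneven ascertainment across participants, and the CSR should note it.

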## 9.2.2 Reactogenicity

Reactogenicity events are solicited AEs that are common and known to occur following administration of this type of study vaccine. The following Toxicity Grading Scales will be used to grade solicited injection site and systemic (subjective and quantitative) reactions:

**Table 5: Injection Site Reactogenicity Grading** 

Injection Site Reaction	Mild (Grade 1)	Moderate (Grade 2)	Severe (Grade 3)
Pain – experienced without touching the injection site (spontaneous discomfort)	Subject is aware of pain, but it does not interfere with daily activity, and if pain medication is used, it is Over the Counter (OTC) and used for less than 24 hours	Subject is aware of pain; there is interference with daily activity or OTC pain medication is used for more than 24 hours	Subject is aware of pain, and it prevents daily activity or pain requires prescription medication
Tenderness-experienced with touching the injection site	Subject is aware of pain, but it does not interfere with daily activity, and if pain medication is used, it is Over the Counter (OTC) and used for less than 24 hours	Subject is aware of pain; there is interference with daily activity or OTC pain medication is used for more than 24 hours	Subject is aware of pain,  and it prevents daily activity or pain requires prescription medication

Injection Site Reaction	Mild (Grade 1)	Moderate (Grade 2)	Severe (Grade 3)
Pruritus	Does not interfere with daily activity	Interferes with daily activity	Prevents daily activity or requires prescription medication
Ecchymosis (Bruising)*	Does not interfere with daily activity	Interferes with daily activity	Prevents daily activity
Erythema (Redness)*	Does not interfere with daily activity	Interferes with daily activity	Prevents daily activity
Edema (Swelling)/Induration (Hardness)*	Does not interfere with daily activity	Interferes with daily activity	Prevents daily activity

\* Will also be measured in mm but size will not be used as halting criteria.

Ecchymosis, erythema and edema/induration as analyzed by measurement will be graded as follows:

**Table 6: Injection Site Reactogenicity Measurements** 

Injection Site Reaction	Small	Medium	Large
Ecchymosis (Bruising)*	<20 mm	20 mm – 50 mm	>50 mm
Erythema (Redness)*	<20 mm	20 mm – 50 mm	>50 mm
Edema (Swelling)/Induration (Hardness)*	<20 mm	20 mm – 50 mm	>50 mm

\* Will not be used as halting criteria.

**Table 7: Subjective Systemic Reactogenicity Grading** 

Systemic (Subjective)	Mild (Grade 1)	Moderate (Grade 2)	Severe (Grade 3)
Feverishness	No interference with daily activity	Some interference with daily activity	Significant interference, prevents daily activity
Fatigue	No interference with daily activity	Some interference with daily activity	Significant interference, prevents daily activity
Malaise	No interference with daily activity	Some interference with daily activity	Significant interference, prevents daily activity

Systemic (Subjective)	Mild (Grade 1)	Moderate (Grade 2)	Severe (Grade 3)
Myalgia*	No interference with daily activity	Some interference with daily activity	Significant interference, prevents daily activity
Arthralgia*	No interference with daily activity	Some interference with daily activity	Significant interference, prevents daily activity
Headache	No interference with daily activity	Some interference with daily activity	Significant interference, prevents daily activity or headache requires prescription medication
Nausea	No interference with daily activity	Some interference with daily activity	Significant interference, prevents daily activity or nausea requires prescription medication

\* Not at injection site.

Oral temperature# will be graded as follows:

Table 8: Quantitative Systemic (Oral Temperature) Reactogenicity Grading

Systemic (Quantitative)	Mild (Grade 1)	Moderate (Grade 2)	Severe (Grade 3)
Fever* – oral†	38.0°C – 38.4°C	38.5°C – 38.9°C	>38.9°C
rever - oran	100.4°F – 101.1°F	101.2°F – 102.0°F	>102.0°F

<sup># Oral temperature assessed on Day 1 prior to the first study vaccination will be considered as baseline.

